6.7. Posttreatment Assessments—Early Study Drug Discontinuation Visit

Participants who prematurely discontinue study drug prior to completing the infusions of the VRC07-523LS and CAP256V2LS, or all 10 doses of VES, as described in Section [6.9.1](#), Criteria for Discontinuation of Study Drug, will complete an ESDD visit within 3 days of informing the investigator/site.

At the ESDD visit, any evaluations showing abnormal results indicating that there is a possible or probable causal relationship with the study drug should be repeated weekly (or as often as deemed prudent by the investigator) until the abnormality is resolved, returns to baseline, or is otherwise explained.

The following assessments will be performed at the ESDD visit:

- Symptom-directed physical examination
- Review of AEs and changes in concomitant medications
- Vital signs (blood pressure, pulse, respiration rate, oxygen saturation, and temperature)
- Body weight

- Obtain blood samples for:
 - Plasma HIV-1 RNA
 - Plasma HIV-1 resistance testing (in case of viral rebound) to VRC07-523LS, CAP256V2LS, and baseline ART
 - Chemistry profile: ALP, AST, ALT, total bilirubin, direct and indirect bilirubin, total protein, albumin, CK, bicarbonate, BUN, calcium, chloride, creatinine, glucose, phosphorus, magnesium, potassium, sodium, uric acid
 - Hematology profile: CBC with differential and platelet count
 - Creatinine clearance according to the Cockcroft-Gault:
$$\text{Female Estimated Creatinine Clearance} = [(140 - \text{age in years}) \times (\text{weight in kg})] / [72 \times (\text{serum creatinine in mg/dL})] \times 0.85$$
 - Whole blood ISG mRNA panel
 - Soluble proteins (cytokines, chemokines, and inflammatory markers)
 - CD4+ and CD8+ T cell absolute count, percentage, and CD4/CD8 ratio
- Obtain urine collection for:
 - Urinalysis
 - Urine pregnancy testing; a positive result will be confirmed with a serum pregnancy test.
 - Urine pregnancy kits will be provided to participants who completed the VRC07-523LS and CAP256V2LS infusion for monitoring as described in Section [6.9.2](#)

6.8. End-of-Study Visit

The end-of-study visit will occur for participants who have completed Period 4A or 4B. The visit will occur 1 week after completion of the last Period 4 visit. For the purpose of scheduling the end-of-study visit, a \pm 3 day window may be used based on the Day 0 visit + the number of postponement days required to confirm ATI eligibility in Period 1, if applicable.

The ART reinitiation after the end-of-study visit will be up to the participant's health care provider discretion.

The following assessments will be performed at the end-of-study visit:

- Symptom-directed physical examination
- Vital signs (blood pressure, pulse, respiration rate, oxygen saturation, and temperature)
- Body weight
- Review of AEs and changes in concomitant medications
- 12-lead ECG
- Obtain urine collection for:
 - Urinalysis
 - Urine pregnancy testing; a positive result will be confirmed with a serum pregnancy test
- Obtain blood samples for:
 - Plasma HIV-1 RNA
 - Plasma HIV-1 resistance testing (in case of viral rebound) to VRC07-523LS, CAP256V2LS, and baseline ART
 - Chemistry profile: ALP, AST, ALT, total bilirubin, direct and indirect bilirubin, total protein, albumin, CK, bicarbonate, BUN, calcium, chloride, creatinine, glucose, phosphorus, magnesium, potassium, sodium, uric acid
 - Hematology profile: CBC with differential and platelet count
 - CD4+ and CD8+ T cell absolute count, percentage, and CD4/CD8 ratio
 - Creatinine clearance according to the Cockcroft-Gault formula:
$$\text{Female Estimated Creatinine Clearance} = [(140 - \text{age in years}) \times (\text{weight in kg})]/72 \times (\text{serum creatinine in mg/dL}) \times 0.85$$
- The following additional ATI remission tests will be required:
 - HIV-specific antibody profiling using plasma
 - Whole blood ISG mRNA panel
 - Soluble proteins (cytokines, chemokines, and inflammatory markers)
 - PBMC sample for testing of viral sensitivity to the VRC07-523LS and CAP256V2LS mAbs
 - PBMC sample for immune cell frequency, activation, and phenotyping
 - PBMC sample for HIV-specific T cell responses

- PBMC sample for latent HIV-1 reservoir
- PBMC sample for active HIV-1 reservoir
- Plasma sample for active HIV-1 reservoir
- From participants who provide additional consent, lymph node and/or GALT (GALT obtained by rectosigmoid biopsy) tissue collection (within window of \pm 5 days) for some or all of the following tests:
 - Immune cell frequency, activation and phenotype, gene expression, and HIV-specific T cell response evaluation (PD and immunology)
 - HIV-1 reservoir measurements (virology)

6.9. Assessments for Early Discontinuation from Study

If a participant should discontinue study dosing as described in Section 6.9.1, they will be required to complete an early study drug discontinuation (ESDD) visit and every attempt should be made to keep the participant in the study and continue to perform study procedures. If the participant is unable to complete all scheduled procedures, for criteria other than those described for study discontinuation in Section 3.5, the participant should be followed by telephone as described in Section 6.9.2.

If a participant has completed all study drug dosing but is unable to complete all subsequent visits at the study site, as scheduled in Periods 3 and 4, for criteria other than those described for study discontinuation in Section 3.5, the participant should be followed by telephone for 250 days after mAb infusion.

At the end of all follow-up monitoring, participants will undergo the end-of-follow-up visit at the study site.

6.9.1. Criteria for Discontinuation of Study Drug

Study drug may be discontinued in the following instances:

- Intercurrent illness that would, in the judgment of the investigator, affect assessments of clinical status to a significant degree. Following resolution of intercurrent illness, the participant may resume study dosing at the discretion of the investigator
- Unacceptable toxicity, or toxicity that, in the judgment of the investigator, compromises the ability to continue study-specific procedures or is considered to not be in the participant's best interest
- Participant request to discontinue for any reason
- Participant noncompliance
- Pregnancy during the study; refer to [Appendix 5](#)

- Discontinuation of the study at the request of Gilead, a regulatory agency or an IRB or IEC
- Participant receives study drug(s) and experiences 1 or more AE or laboratory abnormality as follows:
 - \geq Grade 3 treatment-emergent AE (including new finding of splenomegaly, mucosal petechiae or purpura on physical examination or CRS) judged by the investigator as at least possibly related to study drug, OR
 - \geq Grade 3 confirmed laboratory abnormality (including a confirmed significant drop in platelets to $< 50,000/\text{mm}^3$ and/or confirmed drop of 50% from baseline), unless there is a clear and obvious physiologic explanation for the events (eg, blood in urine occurring in a menstruating female, CK elevation after strenuous exercise, or triglyceride elevation that is nonfasting) judged by the investigators as at least possibly related to study drug, OR
 - A persistent (≥ 72 hours) \geq Grade 2 pyrexia considered related to study drug by the investigator, OR
 - Any SAE considered at least possibly related to study drug

6.9.2. Follow Up and Procedures After Early Discontinuation of Study Drug

After early discontinuation of study drug, for criteria other than those described in Section 3.5 every attempt should be made to keep the participant in the study and continue to perform planned study procedures. Antiretroviral therapy may be restarted at the discretion of the investigator. If participant is unable to complete all scheduled procedures, the participant should undergo the following follow-up procedures:

- If a participant discontinues study drug after having received VES alone, the participant should be followed for 30 days after the last VES dose, to monitor for AEs.
 - The participant will complete the ESDD visit within 3 days of informing the investigator/site. Participants should then be followed with a telephone check-up at 14 days after the last VES dose to monitor for AEs. The end of the monitoring period will be 30 days after the last VES dose and participants will undergo the end-of-follow-up visit at the study site.
- If a participant discontinues study drug after having received CAP256V2LS and VRC07-523LS, and before ATI is initiated, the participant should not start ATI and should be followed for 250 days after mAb infusion.
 - The participant will complete the ESDD visit within 3 days of informing the investigator/site. Participants should be followed with telephone check-ups after the ESDD visit every 4 weeks thereafter to monitor for AEs and retrieve urine pregnancy results. At the end of the monitoring period, participants will undergo the end-of-follow-up visit at the study site.
 - A positive urine pregnancy result will require confirmation with a serum pregnancy test at the study site.

- If a participant discontinues study drug after having received CAP256V2LS and VRC07-523LS, and after ATI is initiated, the participant should undergo the following procedures:
 - If ART is reinitiated, the participant should be followed for 250 days after mAb infusion. An ESDD visit will be completed within 3 days for the last study drug dose. Participants should continue the study visit schedule and undergo all other planned study-related procedures. If participants are not able to attend the visit, participants may then be followed with telephone check-ups every 4 weeks thereafter to monitor for AEs and retrieve urine pregnancy results. At the end of the monitoring period, participants will undergo the end-of-follow-up visit at the study site.
 - A positive urine pregnancy result will require confirmation with a serum pregnancy test at the study site.
 - If ART is not reinitiated (ATI is continued), an ESDD visit will be completed within 3 days of informing the investigator/site and the participant should continue the study visit schedule and undergo all other planned study-related procedures.
- If a participant experiences any AE or reports any unexpected symptoms during telephone check-ups, an unscheduled visit should be arranged to perform the following:
 - Symptom-directed physical examination
 - Vital signs (blood pressure, pulse, respiration rate, oxygen saturation, and temperature)
 - Symptom-directed acquisition of blood and urine samples

Participants may be followed with weekly on-site visits until the AE has been treated successfully. Telephone check-ups every 4 weeks will resume thereafter, as applicable.

6.9.3. Follow Up and Procedures After Treatment Completion

If a participant completes all doses of study drug but is unable to complete all of the subsequent visits at the study site, as scheduled in Periods 3 and 4, for criteria other than those described in Section 3.5, the participant should be offered follow up for 250 days after mAb infusion. During this period, participants should be followed with telephone check-ups every 4 weeks to monitor for AEs and retrieve urine pregnancy results (kits to be provided at the last study site visit and a positive urine pregnancy result will require confirmation with a serum pregnancy test at the study site). At the end of the monitoring period, participants will undergo the end-of-follow-up visit at the study site.

If a participant experiences any AE or reports any unexpected symptoms during telephone check-ups, an unscheduled visit should be arranged to perform the following:

- Symptom-directed physical examination
- Vital signs (blood pressure, pulse, respiration rate, oxygen saturation, and temperature)
- Symptom-directed acquisition of blood and urine samples

Participants may be followed with weekly on-site visits until the AE has been treated successfully. Telephone check-ups every 4 weeks will resume thereafter, as applicable.

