To mitigate these risks, plasma viral load and CD4+ T cell count will be measured frequently during ATI, and ART will be promptly reinitiated according to the protocol-defined algorithm. Participants will also be monitored for AEs, and ART will be reinitiated if these are judged (by the investigator and/or sponsor) to be related to the ATI. The initial selection of participants who have a documented detection during acute HIV infection and timing of ART initiation, durable viral suppression for at least 12 consecutive months prior to the screening visit, and the availability of a fully active alternative ART regimen, in the event of discontinuation of the current ART regimen with development of resistance, will further minimize the risks of ATI.

Potential benefits include reduction of the latent HIV-1 viral reservoir, enhanced immune control of virus producing cells, and finally the combination of these effects on HIV-1 viral control (measured as plasma virus rebound and viral load set-point) in the absence of ART. There are no direct benefits to participants participating in this study.

During a pandemic, additional potential risks to the conduct of the study may include adequate study drug availability, interruptions to the study visit schedule, and adherence to protocol-specified treatment regimen, safety monitoring or laboratory assessments. Refer to [Appendix 7](#) for further details on the risks and risk mitigation strategy.

Considering the above, the benefit-risk balance for this study is considered positive.

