- HIV-specific antibody profiling using plasma (**Days 126 and 133**)
- Whole blood ISG mRNA panel (**Days 56, 57, 126, and 127**)
- Soluble proteins (cytokines, chemokines, and inflammatory markers) (**Days 56, 57, 63, 126, 127, and 133**)
- CD4+ and CD8+ T cell absolute count, percentage, and CD4/CD8 ratio (**Days 42, 56, 70, 84, 98, 112, 126, and 133**)
- PBMC sample for immune cell frequency, activation, and phenotyping (**Days 56, 57, 63, 126, 127, and 133**)
- PBMC sample for HIV-specific T cell responses (**Days 63 and 133**)
- Serum VRC07-523LS PK collection (**Days 56, 84, 112, and 133**)
- Serum CAP256V2LS PK collection (**Days 56, 84, 112, and 133**)
- Plasma dolutegravir PK collection (**Days 56, 84, 112, and 133**)
- Plasma sample for active HIV-1 reservoir (**Days 56, 57, 126, 127, and 128**)
- PBMC sample for active HIV-1 reservoir (**Days 56, 57, 126, 127, and 128**)

- Obtain urine collection for:
 - Urinalysis (**Day 42 and at each visit every 2 weeks thereafter**)
 - Urine pregnancy testing; a positive result will be confirmed with a serum pregnancy test. If the serum pregnancy test is positive, the participant will discontinue from study drug (**Day 42 and at each visit every 4 weeks thereafter**)
- Birth control will be checked and replaced, if required.
- Ongoing eligibility assessment prior to the participant being administered study drug on site (**Days 42, 56, 70, 84, 98, 112, and 126**)
 - Known HIV-1 seronegative sexual partners of enrolled study participants may be referred for HIV PrEP to decrease risk of HIV transmission during ATI.
- Adverse events and changes in concomitant medications will be assessed and recorded. Participants will be reminded to report all symptoms, including flu-like symptoms (eg, fatigue, pyrexia, chills, myalgia, joint pain, or headache) or other unexpected symptoms

6.5. Posttreatment Assessments—Period 3

Participants will have up to 14 study visits every 2 weeks for a total of 29 weeks.

No study drug (VES, VRC07-523LS, or CAP256V2LS) will be administered during this period.

No ART will be administered during this period and ATI will continue. If the ART restart criteria are met, the participant will stop Period 3, complete the end-of-Period 3 visit (Section 6.5.2), and may restart ART in Period 4A.

Upon completion of Period 3, all participants will be required to complete an end-of-Period 3 visit prior to moving into Period 4.

Table 5. Period 3 Study Visits and Study Drug Administration

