6.9.4. End-of-Follow-Up Visit

At the end of the monitoring period described in Sections [6.9.2](#) and [6.9.3](#), participants will complete a final visit at the study site. All participants will complete the following procedures:

- Symptom-directed physical examination
- Vital signs (blood pressure, pulse, respiration rate, oxygen saturation, and temperature)
- Body weight
- Review of AEs and changes in concomitant medications
- 12-lead ECG
- Obtain urine collection for:
 - Urinalysis
 - Urine pregnancy testing; a positive result will be confirmed with a serum pregnancy test.
- Obtain blood samples for:
 - Plasma HIV-1 RNA
 - Plasma HIV-1 resistance testing (in case of viral rebound) to VRC07-523LS, CAP256V2LS, and baseline ART
 - Chemistry profile: ALP, AST, ALT, total bilirubin, direct and indirect bilirubin, total protein, albumin, CK, bicarbonate, BUN, calcium, chloride, creatinine, glucose, phosphorus, magnesium, potassium, sodium, uric acid
 - Hematology profile: CBC with differential and platelet count
 - CD4+ and CD8+ T cell absolute count, percentage, and CD4/CD8 ratio
 - Creatinine clearance according to the Cockcroft-Gault formula:
Female Estimated Creatinine Clearance =
$$[(140 - \text{age in years}) \times (\text{weight in kg})] / [72 \times (\text{serum creatinine in mg/dL})] \times 0.85$$

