Appendix 2b. Follow-up Period: Study Procedures Table

[figure not shown]
	Follow-up period for participants who discontinued study drug after having received VES alone ^{a,b}	Follow-up period for participants who discontinued study drug after having received CAP256V2LS and VRC07-523LS, and before ATI is initiated ^{b,c}	Follow-up period for participants who discontinued study drug after having received CAP256V2LS and VRC07-523LS, and after ATI is initiated ^{c,d,e}	Follow-up period for participants who completed all doses of study drug but is unable to complete all of the subsequent visits at the study site ^{b,f}	End-of-Follow-up visit ^b
Telephone check-up	X	X	X	X	
Symptom-directed physical exam	X ^g	X ^g	X ^g	X ^g	X
Vital signs	X ^g	X ^g	X ^g	X ^g	X
Symptom-directed acquisition of blood and urine samples	X ^g	X ^g	X ^g	X ^g	
Body weight					X
Review of AEs and changes in concomitant medications	X	X	X	X	X
12-Lead ECG					X
Urinalysis					X
Urine pregnancy test		X ^h	X ^h	X ^h	X
Plasma HIV-1 RNA					X
Plasma resistance testing to VRC07-523LS, CAP256V2LS, and baseline ART					X

	Follow-up period for participants who discontinued study drug after having received VES alone ^{a,b}	Follow-up period for participants who discontinued study drug after having received CAP256V2LS and VRC07-523LS, and before ATI is initiated ^{b,c}	Follow-up period for participants who discontinued study drug after having received CAP256V2LS and VRC07-523LS, and after ATI is initiated ^{c,d,e}	Follow-up period for participants who completed all doses of study drug but is unable to complete all of the subsequent visits at the study site ^{b,f}	End-of-Follow-up visit ^b
Chemistry					X
Hematology					X
CD4+ and CD8+ T cell absolute count, percentage, and CD4/CD8 ratio					X
Creatinine clearance					X

AE = adverse event; ART = antiretroviral therapy; ATI = analytical treatment interruption; ECG = electrocardiogram; ESDD = early study drug discontinuation; mAb = monoclonal antibody; VES = vesatolimod

- a Participants should be followed with a telephone check-up at 14 days after the last VES dose to monitor for AEs. The end of the monitoring period will be 30 days after the last VES dose and participants will undergo the end-of-follow-up visit at the study site.
- b All follow-up visits/calls are to be completed within \pm 3 days of the protocol-specified visit date.

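### A woman who has finished dosing and is still off ART can move to telephone follow-up with no scheduled HIV-1 RNA or CD4 until about Day 257

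*Protocol*

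**What the plan says.** Section 6.9.3 applies to a participant who has received all study drug but cannot complete the later site visits, for reasons other than those in Section 3.5. She is offered follow-up to 250 days after the antibody infusion, during which "participants should be followed with telephone check-ups every 4 weeks to monitor for AEs and retrieve urine pregnancy results". The fourth column of Appendix 2b, for a participant who "completed all doses of study drug but is unable to complete all of the subsequent visits at the study site", adds "Review of AEs and changes in concomitant medications" to the calls, with examination, vital signs and samples only if she reports an event or symptom. The HIV-1 RNA and CD4 rows are marked only under the end-of-follow-up visit. This agrees with Section 6.9.4, under which "participants will complete a final visit at the study site" at the end of monitoring. Footnote f, which governs the fourth column, sets no condition on ART. The same rule is repeated in the synopsis, Figure 2 footnote g, Section 3.2 and Section 6.9.

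On ART status in Period 3, Section 6.5 says: "No ART will be administered during this period and ATI will continue".

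Section 6.9.2 deals with the neighbouring case, a woman who stops study drug early after ATI has begun. Its text has two branches. In the first, "If ART is reinitiated, the participant should be followed for 250 days after mAb infusion", with telephone calls if she cannot attend. In the second, where ATI continues, an early-discontinuation visit is done "and the participant should continue the study visit schedule and undergo all other planned study-related procedures"; no telephone option is given.

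Section 1.5 lists the ATI safeguards: "plasma viral load and CD4+ T cell count will be measured frequently during ATI, and ART will be promptly reinitiated" according to the protocol's algorithm.

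**The concern.** This is a participant-safety matter. Of the ART restart criteria in Sections 3.2 and 6.6, three need laboratory results: at least 1,000 copies/mL for 8 consecutive weeks without a 0.3 log10 fall, confirmed RNA above 100,000 copies/mL, and confirmed CD4 below 350 cells/µL. On the telephone path none of these results is scheduled. What still works is restart for pregnancy, on request or at discretion.

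The timing is unfavourable. Section 1.4.3 predicts that VRC07-523LS stays above 20 µg/mL through the end of Period 2 and is subtherapeutic in Period 3, and Section 1.4.2 expects CAP256V2LS to fall below therapeutic levels in Period 3 as well. The gap therefore opens when antibody cover is expected to wane. Section 1.5 names the risks of rebound as resistance, CD4 decline, retroviral symptoms and transmission to others.

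**Working it through.** No sample size or error rate is involved; the check is calendar arithmetic. Days are nominal and ignore the ±3-day windows.

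**Inputs**
- Antibody infusion: Day 7 (Figure 2 footnote l).
- Length of follow-up: 250 days after infusion (6.9.3).
- Last Period 2 visit: Day 133, with CD4 taken (6.4.1).
- Period 3 RNA: every 2 weeks from Day 147. Period 3 CD4: Day 147 and every 4 weeks (6.5.1).
- Postponement moves the Period 2 and 3 visits but not the infusion (6.4.1, 6.5.1).

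**End of follow-up.** 7 + 250 = Day 257.

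**Worst case: exit after Day 133, no postponement**
- Gap: 257 − 133 = 124 days; 124 / 7 = 17.7 weeks.
- RNA missed: Days 147, 161, 175, 189, 203, 217, 231, 245 = 8.
- CD4 missed: Days 147, 175, 203, 231 = 4.
- The RNA figure takes Period 2 virology as weekly, as Section 3.2 says. If the last Period 2 RNA is Day 126, as the 2-weekly list in 6.4.1 implies, the RNA gap is 257 − 126 = 131 days.

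**Postponed ATI.** Section 6.3.3 allows up to 4 weeks after the last VES dose, then up to a further 4 weeks. This can be read in two ways. Counted from the Day 28 dose, ATI starts by Day 28 + 28 = 56, which is 56 − 35 = 21 days late, or 21 + 28 = 49 days with the extension. Counted as a shift of the whole schedule, the delay is 28 or 56 days.

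| Delay (days) | Last Period 2 visit | Gap to Day 257 | RNA missed | CD4 missed |
|---|---|---|---|---|
| 0 | 133 | 124 | 8 | 4 |
| 21 | 133 + 21 = 154 | 103 | 7 | 4 |
| 28 | 133 + 28 = 161 | 96 | 6 | 3 |
| 49 | 133 + 49 = 182 | 75 | 5 | 3 |
| 56 | 133 + 56 = 189 | 68 | 4 | 2 |

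**Later exits, no postponement.** After last visits on Days 147, 161, 175, 189, 203, 217, 231 and 245, 257 minus the visit day gives 110, 96, 82, 68, 54, 40, 26 and 12 days. CD4 is taken at alternate visits, so the time since the last CD4 can be 14 days longer.

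**The 8-week criterion.** The criterion counts consecutive weeks, so weeks before exit count too. Suppose a woman has been at or above 1,000 copies/mL for 3 weeks at her last visit on Day 217. She needs 5 more weeks: 217 + 35 = Day 252, inside her 40-day gap. Gaps shorter than 56 days therefore do not rule this criterion out.

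**The case against.** The strongest reply is that the path is narrow and not without protection. Section 3.5 removes women who ask to leave, are noncompliant, or have significant illness or toxicity. What remains is women who finished dosing, are off ART and still cannot attend, from about 25 enrolled. Restart at discretion or on request applies throughout ATI, any event or symptom reported by telephone prompts a visit, and nothing forbids extra sampling. Appendix 2a footnote x is a standing instruction to test weekly after a confirmed value of 50 copies/mL or more. All of this stands, and it limits how many women are exposed. It does not close the gap. Footnote x is neither suspended nor repeated in 6.9.3, and it starts only once a rebound has been measured. A new asymptomatic rebound or a silent CD4 fall triggers none of these safeguards.

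A reader might infer that 6.9.3 flatly contradicts 6.9.2. The documents do not go that far. The two sections govern different groups, 6.9.2 does not say what happens if a woman who stays off ART cannot attend, and Appendix 2b footnote c words the telephone option for the post-ATI column without an ART condition, although footnotes d and e supply it. The accurate description is an inconsistency in protection for the same ATI exposure.

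A reader might also infer that the efficacy analysis is compromised. SAP Section 6.3 does censor a woman whose closing RNA is high but unconfirmed. That follows from a rebound definition applied to everyone, for a secondary descriptive endpoint, and is a separate matter.

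Finally, SAP Section 2.3 indicates that the last end-of-Period 3 visit has already taken place. An amendment now would come too late for women who left in Period 2 or 3; that does not alter what the protocol allowed.

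**Conclusion.** The point holds and should be fixed. As written, 6.9.3 and the fourth column of Appendix 2b allow a woman in ATI to go without scheduled HIV-1 RNA or CD4 until about Day 257. The worst case is 124 days with 8 RNA and 4 CD4 tests missed. With ATI postponed it is about 96 to 103 days (4 weeks) or 68 to 75 days (a further 4 weeks), depending on the reading of 6.3.3, and later exits shorten it.

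Any of the laboratory restart criteria could be met unseen in that time. It would be wrong to infer that the 8-week criterion is at risk only when the gap exceeds 56 days.

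The figures assume nominal visit days, exit before Day 257, and no ART restart or unscheduled sampling in between. The number affected is probably small. The documents give none, so no expected count of missed rebounds can be stated.

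**What to change.** In Section 6.9.3, the fourth column of Appendix 2b with footnote f, and the places that repeat the rule (synopsis, Figure 2 footnote g, Sections 3.2 and 6.9), allow telephone-only follow-up only after ART has been restarted. A woman who stays off ART keeps HIV-1 RNA every 2 weeks, weekly after a confirmed value of 50 copies/mL or more, and CD4 every 4 weeks. Sampling may be at the site or at a local laboratory. The latter is a new permission, since Appendix 7 allows local laboratories only in a pandemic. If neither is feasible, she is offered ART restart under the existing discretion criterion. In Appendix 2b footnote c, add the condition that ART has been reinitiated for the post-ATI column.

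The cost is one conditional sentence, repeated where the rule is restated, and local sampling arrangements for the few women affected. Other participants' visits and the primary analysis do not change. A supplementary Kaplan-Meier analysis of unconfirmed closing values is a separate option and is not needed here.
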